### **7.2.2 Descriptive analyses**

Commercially Confidential Information

### **7.2.3 Statistical model, assumptions and hypotheses**

#### **Dose-response effect**

Commercially Confidential Information

Commercially Confidential Information

### **7.2.3.1 Model checking procedures**

Commercially Confidential Information

### **7.2.3.2 Graphical presentation of results**

The model predicted relationship curve between dose and PK parameter along with its corresponding 95% CI will be presented for any nonlinear models.

## **7.3 Exploratory objectives**

Commercially Confidential Information

### **7.3.1 Variables**

Commercially Confidential Information

Comercially Confidential Information

### **7.3.2 Descriptive analyses**

Comercially Confidential Information

### **7.3.3 Descriptive analyses**

Comercially Confidential Information

Commercially Confidential Information

## **8 Statistical methods for safety and tolerability data**

All subjects within the full analysis set will be included in the safety data analysis.

Safety summaries (tables, figures) include only data from the on-treatment period with the exception of baseline data which will also be summarized where appropriate (e.g., when change from baseline is used). In addition, a separate summary for any deaths including on treatment and post treatment deaths will be provided. In particular, summary tables for adverse events (AE) will summarize only on-treatment events.

The on-treatment period lasts from the date of first administration of study treatment to 7 days after the date of the last actual administration of any study treatment.

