9.2 Study completion and post-study treatment

Based on the benefit of LNP023 treatment observed in the ongoing phase II studies (CLNP023X2201 and CLNP023X2204), a roll-over extension program (REP), study CLNP023C12201B, has been implemented to ensure long-term post-trial access for all PNH patients completing any of the phase II or phase III studies with LNP023. Study patients who completed study treatment and who demonstrated benefit from LNP023 treatment will have the option to join this roll-over extension program.

Study completion is defined as when the last subject finishes their study completion visit (EoT for patients joining the REP), and any repeat assessments associated with this visit have been documented and followed-up appropriately by the Investigator, or in the event of an early study termination decision, the date of that decision.

Randomized and/or treated subjects not joining the REP should have a safety follow-up call conducted 30 days after last administration of study treatment. The information collected is kept as source documentation. All SAEs reported during this time period must be reported as described in [Section 10.1.3](#) and the SoM. Documentation of attempts to contact the subject should be recorded in the source documentation.

Continuing care should be provided by the investigator and/or referring physician based on subject availability for follow-up.

10 Safety monitoring and reporting

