 - Dose not changed
 - Dose Reduced/increased
 - Drug interrupted/withdrawn
6. its outcome:
 - a. not recovered/not resolved
 - b. recovered/resolved
 - c. recovering/resolving
 - d. recovered/resolved with sequelae
 - e. fatal, or unknown

Conditions that were already present at the time of informed consent should be recorded in medical history of the subject.

Adverse events (including lab abnormalities that constitute AEs) should be described using a diagnosis whenever possible, rather than individual underlying signs and symptoms.

Adverse event monitoring should be continued for at least 30 days following the last dose of study treatment.

Once an adverse event is detected, it must be followed until its resolution or until it is judged to be permanent (e.g. Continuing at the end of the study), and assessment must be made at each visit (or more frequently, if necessary) of any changes in severity, the suspected relationship to the interventions required to treat it, and the outcome.

Information about adverse drug reactions for the investigational drug can be found in the Investigator Brochure (IB).

Abnormal laboratory values or test results constitute adverse events only if they fulfill at least one of the following criteria:

- they induce clinical signs or symptoms
- they are considered clinically significant
- they require therapy

Clinically significant abnormal laboratory values or test results must be identified through a review of values outside of normal ranges/clinically notable ranges, significant changes from baseline or the previous visit, or values which are considered to be non-typical in subjects with the underlying disease.

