10.1.3 SAE reporting

To ensure subject safety, every SAE, regardless of causality, occurring after the subject has provided informed consent and until 30 days following the last administration of study treatment must be reported to Novartis safety within 24 hours of learning of its occurrence. Detailed instructions regarding the submission process and requirements are to be found in the

investigator folder provided to each site. The 30 day safety follow up will be completed as a part of the REP for patients joining roll-over extension.

All follow-up information for the SAE including information on complications, progression of the initial SAE and recurrent episodes must be reported as follow-up to the original episode within 24 hours of the investigator receiving the follow-up information. An SAE occurring at a different time interval or otherwise considered completely unrelated to a previously reported one must be reported separately as a new event.

If the SAE is not previously documented in the Investigator's Brochure or Package Insert (new occurrence) and is thought to be related to the study treatment, a CMO & PS Department associate may urgently require further information from the investigator for health authority reporting. Novartis may need to issue an Investigator Notification (IN) to inform all investigators involved in any study with the same study treatment that this SAE has been reported.

Suspected Unexpected Serious Adverse Reactions (SUSARs) will be collected and reported to the competent authorities and relevant ethics committees in accordance with EU Guidance 2011/C 172/01 or as per national regulatory requirements in participating countries.

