12.5.2 Safety endpoints

For all safety analyses, the full analysis set will be used.

Commercially Confidential Information

Safety summaries (tables, figures) include only data from the on-treatment period with the exception of baseline data which will also be summarized where appropriate (e.g., when change from baseline is used). In addition, a separate summary for any deaths including on treatment and post treatment deaths will be provided. In particular, summary tables for adverse events (AE) will summarize only on-treatment events.

The on-treatment period lasts from the date of first administration of study treatment to 30 days after the date of the last actual administration of any study treatment.

Adverse events

All information obtained on adverse events will be displayed as described above taking into account the study design involving sequences,

Commercially Confidential Information

Listings will be down to patient level. The number (and percentage) of patients with treatment

emergent adverse events (events starting after the first dose of study medication or events present prior to start of double-blind treatment but increased in severity based on preferred term) will be summarized in the following ways:

- by treatment dose group including split by first and second four weeks in second period, primary system organ class and preferred term.

Commercially Confidential Information

Separate summaries will be provided for study medication related adverse events, death, serious adverse events, other significant adverse events leading to study and/or investigational drug discontinuation and any adverse events leading to dose adjustment.

A subject with multiple adverse events within a primary system organ class is only counted once towards the total of the primary system organ class. Adverse events which will be counted for a specific treatment period are those which are treatment-emergent. These events are those with an onset after the start of the dose level treatment period, or which were present prior to the start of the treatment period but increased in severity, changed from being not suspected to being suspected of study drug relationship, or developed into SAEs after the start of the dosing period.

Vital signs

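### The SAP ends the on-treatment safety window 7 days after last dose where the protocol says 30, so events from days 8 to 30 drop out of the AE summary tables

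*SAP*

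**What the plan says.** The SAP's safety section defines the period as follows: "The on-treatment period lasts from the date of first administration of study treatment to 7 days after the date of the last actual administration". The protocol's section on safety endpoints (12.5.2) defines it as follows: "The on-treatment period lasts from the date of first administration of study treatment to 30 days after the date of the last actual administration". Apart from the number of days, the sentence is the same.

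Both documents tie the safety output to this period. In the SAP's words, "summary tables for adverse events (AE) will summarize only on-treatment events", and Protocol 12.5.2 carries the same restriction. The only stated exceptions are baseline values and a separate summary of deaths, which includes deaths after treatment.

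The protocol's collection rules run to day 30:
- Section 10.1.1: "Adverse event monitoring should be continued for at least 30 days following the last dose of study treatment".
- Section 10.1.3 covers every SAE from consent "until 30 days following the last administration of study treatment must be reported to Novartis safety within 24 hours".
- Section 9.2: patients who do not join the REP "should have a safety follow-up call conducted 30 days after last administration of study treatment".

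SAP Section 1.1 presents the SAP as carrying out the analysis planned in the protocol. Its visible text does not mention or justify a shorter window.

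**The concern.** In the protocol, the analysis window and the collection period both end at day 30. In the SAP, the analysis window ends 23 days before collection does. An event on day 15 after the last dose must be recorded, and if serious reported within 24 hours, yet it would be counted in none of the AE, SAE, drug-related or discontinuation summaries.

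The protocol does not treat those days as empty follow-up. Section 4.1 explains the two-week taper by the possibility that hemolysis worsens once the drug is withdrawn. Section 9.1.1 asks for close observation after stopping, naming LDH, hemoglobin and thrombosis among the things to watch, and lists measures to consider if serious hemolysis occurs. Leaving out most of the follow-up after stopping would understate the risk of coming off treatment. The patients concerned are those who stop, including non-responders who taper after Period 2 instead of continuing.

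**Working it through.** The point rests on comparing two definitions, and neither document calculates a figure for it.

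**Inputs**

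| Item | Value | Source |
|---|---|---|
| End of on-treatment window, SAP | last dose + 7 days | SAP 8 |
| End of on-treatment window, protocol | last dose + 30 days | Protocol 12.5.2 |
| AE monitoring | at least 30 days after last dose | Protocol 10.1.1 |
| SAE reporting | to 30 days after last dose | Protocol 10.1.3 |
| Follow-up call, patients not joining the REP | day 30 after last dose | Protocol 9.2 |
| End-of-study visit | one week after last dose | Protocol summary, Section 3 |
| Last taper visit and end-of-study visit | days 99 and 106, or 771 and 778 | Protocol Table 8-1 |

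**Step 1: days lost.** 30 − 7 = 23 days (days 8 to 30), and 23 / 30 = 76.7% of the post-dose period.

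**Step 2: where the cut falls.** Table 8-1 gives 106 − 99 = 7 and 778 − 771 = 7. Counting from the last taper visit as the last dose, the SAP window closes at the end-of-study visit: day 106 for patients who stop after Period 2 and day 778 for those who stop after Period 3. The day-30 call falls at 99 + 30 = 129 or 771 + 30 = 801. The SAP window therefore leaves out the whole interval between the end-of-study visit and the call.

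**Step 3: which output is affected.** Because AE tables hold only on-treatment events, a non-fatal event in those 23 days is in the protocol's tables and absent from the SAP's. A fatal event is absent from the SAP's AE tables but is kept in the death summary. Nothing in the visible text removes events from listings.

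**Step 4: effect on a table.** The documents give no expected event counts, so this is an illustration with one hypothetical SAE on days 8 to 30:
- All patients, assuming 10: 1 / 10 = 10% under 30 days, 0 / 10 = 0% under 7 days.
- One sequence, assuming 5 patients from the 1:1 randomization: 1 / 5 = 20% against 0%.

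The main AE table in SAP 8.2 is split by dose within period, so its denominators may differ from both. The table of adverse events of special interest is by treatment sequence, where the second line would apply if that table uses the same window.

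**The case against.** The conflict between the two numbers is not in dispute. The strongest case on the other side is that it matters less than it appears.

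- **Some output survives.** Deaths are summarized separately, listings are not cut, and the sponsor reviews each SAE individually under Protocol 9.1.4. In a non-confirmatory study of about 10 patients, listings carry much of the safety information. This is true, but the summary and disclosure tables are what most readers will see.
- **Not all 23 days yield database records.** Protocol 9.2 keeps the call information in source documents, so a non-serious AE learned only at the call might not reach the database. The end-of-study visit is the last scheduled visit for patients who complete the schedule. This narrows the certain loss to non-fatal SAEs. It does not override the duty in 10.1.1 to record AEs in the CRF and monitor for at least 30 days. Patients who stop early are also asked in 9.1.1 to keep attending scheduled visits.
- **REP entrants are outside the gap.** Under Protocol 10.1.3 their 30-day follow-up takes place in the REP. This stands, and the number of remaining patients is unknown.
- **Timing and causality.** The documents do not show that rebound events occur on days 8 to 30, and the taper and first drug-free week remain inside the SAP window. Protocol 10.1.1 says events due to disease progression will usually be judged not suspected, so many would be missing from the drug-related table under either window. They would still belong in the AE and SAE tables.
- **A reason may exist.** SAP Section 4 is partly redacted, the SAP cites protocol v02 of 03-Aug-2021, and the version of the protocol reviewed is not visible. Seven days also matches the end-of-study visit, so the choice may have been deliberate. Either explanation would still have to be documented.

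**Conclusion.** The concern holds. Followed as written, the SAP takes 23 of 30 post-dose days (77%) out of the AE summaries for each patient who stops and does not join the REP, contrary to the protocol it says it implements. The loss is clearest for non-fatal SAEs, whose reporting to day 30 is mandatory, and somewhat less certain for non-serious AEs. The 77% is a share of follow-up days, not of events or risk, and the 10% and 20% figures assume one hypothetical SAE and full enrollment of 10 patients.

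The primary endpoint, the efficacy criterion, data collection and SAE reporting are untouched. The conclusion assumes that no redacted text redefines the window. It should be corrected before database lock, because the SAP would otherwise produce safety tables that differ from those the protocol promises.

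**What to change.** In SAP Section 8, replace 7 days with 30 days after the last administration, to match Protocol 12.5.2 and the collection period. Two additions make this workable:

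- State where the window ends for patients entering the REP. Ending it at the first REP dose is a practical suggestion; it is in neither document, and the main fix does not depend on it.
- State that the treatment-emergent tables for the public registries and the table of adverse events of special interest use the same window.

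If 7 days was intended, record and justify it as a change from the protocol, and add a separate table of events on days 8 to 30. In either case, confirm which protocol version the SAP was written against.

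The cost is one number and its programming. No new data, visits or patients are needed, and a few more events may appear in the tables.

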### **8.1 Variables**

Adverse events, vital signs (blood pressure, pulse rate, body temperature), ECG intervals, laboratory measurements, as well as subject demographics, baseline characteristics, treatment information, transfusion and patient diary data.

### **8.2 Descriptive analyses**

#### **Subject demographics and other baseline characteristics**

All data for background and demographic variables will be listed by treatment sequence and subject. Summary statistics will be provided for all subjects, as well as for each treatment sequence. For baseline characteristics the values at the baseline visit will be listed/summarized.

Categorical data will be presented as frequencies by treatment sequence. For continuous data, mean, standard deviation, median, minimum, and maximum will be presented.

Relevant medical history, current medical conditions, results of laboratory screens, drug tests and any other relevant information will be listed by treatment sequence and subject.

Relevant medical history and current medical conditions will be summarized by reported term, system organ class (SOC) and preferred term (PT), by treatment sequence.

#### **Treatment**

Data for a) prior and concomitant medications, b) surgical/medical procedures and investigations and c) vaccinations and prophylactic antibiotics will be listed separately by treatment sequence and subject.

The duration of exposure in days (including half days) to each dose of LNP023 will be summarized by means of descriptive statistics.

Concomitant medications and significant non-drug therapies prior to and after the start of the study treatment will be summarized according to the Anatomical Therapeutic Chemical (ATC) classification system, by treatment sequence group. In addition, the incidence of on-study medical/surgical procedures and investigations by preferred term will be displayed. A subject with multiple medical/surgical procedures and investigations with the same preferred term is counted only once for that preferred term and treatment.

Number and percentage of subjects who received the vaccination during Screening period will be summarized.

### **Vital signs**

All vital signs data will be listed by treatment sequence, subject, and visit/time and if ranges are available abnormalities (and relevant orthostatic changes) will be flagged. Summary statistics will be provided as described in [Section 4](#).

### **ECG evaluations**

All ECG data will be listed by treatment sequence, subject and visit/time, abnormalities will be flagged. Summary statistics will be provided as described in [Section 4](#).

### **Clinical laboratory evaluations**

All laboratory data will be listed by treatment, subject, and visit/time and if normal ranges are available abnormalities will be flagged. A separate listing is provided presenting all parameters in a subject with any abnormal values. Summary statistics will be provided as described in [Section 4](#).

### **Adverse events**

All information obtained on adverse events will be displayed as described in [Section 4](#) taking into account the study design involving sequence.

The number and percentage of subjects with adverse events will be tabulated by body system and preferred term with a breakdown by dose for each period separately.

An adverse event starting in one period and continuing into the next period is counted only in the onset period. A subject with multiple adverse events within a body system and treatment period is only counted once towards the total of this body system and treatment.

Separate summaries will be provided for study medication related adverse events, death, serious adverse events, other significant adverse events leading to study and/or investigational drug discontinuation and any adverse events leading to dose adjustment.

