| Concomitant medications | | | | | | | | X | | | | | |
| Comments | | | | | | | | X | | | | | |
| Study completion | | | | | | | | X ¹⁶ | | | | | X |

^X Assessment to be recorded in the clinical database or received electronically from a vendor

^S Assessment to be recorded in the source documentation only

¹ Visit structure given for internal programming purpose only

² Visit only applicable for Sequence 1 and 2 patients who do not have 40% reduction in LDH level at day 15

³ Randomization should only occur once eligibility is confirmed.

⁴ Serum pregnancy test required at screening and EOS, urine pregnancy test at further time points.

⁵ LNP023 to be administered daily b.i.d

⁶ To be completed pre-LNP023 dose, if applicable.

⁷ Done only if no medical data is available that could be used for inclusion purpose

Commercially Confidential Information

⁹ Samples collected only if patient did not complete PK sample collection at day 16

¹⁰ Start of LNP023 down-titration for patients who do not participate in extension period 3

¹¹ A safety follow-up call 30 days after last treatment administered will be performed for patients not joining REP

¹² C3 deposition, clone size, type III PNH cells

¹³ Start of LNP023 down-titration for patients who discontinue LNP023 treatment. EoS visit for patients joining REP

¹⁴ Baseline visits can be conducted on the same day as the last screening visit, if the last screening visit is not more than 7 days prior to Day 1

¹⁵ For patients not joining REP

¹⁶ Assessments to be performed only for patients joining REP and complete study at EoT visit

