12.5 Analysis of secondary endpoints

Assessment of plasma pharmacokinetics is a secondary endpoint but the analyses for it are described below in [Section 12.5.3](#). Assessing the dose-response effect on LDH and other parameters associated with PNH associated hemolysis is the first secondary objective.

Mixed effect modelling will be performed for LDH.

Commercially Confidential Information

Commercially Confidential Information

Baseline LDH will be calculated as the average of the last three screening values prior to randomization. The subject term will be considered as random so as to allow recovery of between subject information.

Commercially Confidential Information

The same mixed modelling approach will be used for other key continuous response secondary endpoint variables apart from LDH that are markers of intravascular and extravascular hemolysis, or are markers of thrombosis, as well as for PK parameters excluding Tmax (see [Section 12.5.3](#)). In these cases, except for PK parameters, the baseline covariate is the average of all pre-treatment values.

Data may be transformed in order to meet underlying normality and homoscedasticity assumptions. In case early escalation gives data only to two weeks for some patients, the modelling will be adjusted to suit, in the first instance looking only at Week 2 data for all patients.

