### **1.4 Study design and treatment**

This is a non-confirmatory, randomized, open-label, multicenter, efficacy, safety, pharmacokinetic and pharmacodynamic study assessing CCI LNP023 doses, in adult PNH patients with active hemolysis.

At least 10 patients will be included in the study, as replacement can occur if any patient withdraws for reasons unrelated to safety or lack of efficacy.

Total study duration from screening until EOS is approximately 2.5 years. This three-period study includes: a screening phase of up to 8 weeks, a baseline visit, Day 1 (first day that the investigational drug is given), a 4-week treatment period of LNP023 at the first dose in the assigned sequence (Period 1), an 8-week treatment period at the second dose in the assigned sequence (Period 2), an approximately 2 year extension Period 3, followed by a taper down period of 2 weeks, an end of study visit and a safety follow up call performed 30 days post end of treatment.

Patient will be randomized to sequence 1 or sequence 2 in ratio 1:1.

Commercially Confidential Information

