### **Adverse event reporting for Clinical Trial Safety Disclosure (CTSD)**

For the legal requirements of ClinicalTrials.gov and EudraCT, two required tables, 1) on treatment-emergent adverse events which are not serious adverse events with an incidence greater than 5% and 2) on treatment-emergent serious adverse events and SAE suspected to be related to study treatment, will be provided by SOC and PT on the full analysis set population. These tables will be produced by Novartis. The value of the cutoff value X will be decided with the team when disclosure tables are prepared.

The summary will be done by dose and Period as described in [Section 4](#).

If for a same patient, several consecutive AEs (irrespective of study treatment causality, seriousness and severity) occurred with the same SOC and PT:

- a single occurrence will be counted if there is  $\leq$  1-day gap between the end date of the preceding AE and the start date of the consecutive AE
- more than one occurrence will be counted if there is  $>$  1-day gap between the end date of the preceding AE and the start date of the consecutive AE.

For occurrence, the presence of at least one SAE / SAE suspected to be related to study treatment / non-SAE has to be checked in a block e.g., among AE's in a  $\leq$  1-day gap block, if at least one SAE is occurring, then one occurrence is calculated for that SAE.

The number of deaths resulting from SAEs suspected to be related to study treatment and SAEs irrespective of study treatment relationship will be provided by SOC and PT.

Adverse events of special interest (AESI) definitions are found in the compound electronic Case Retrieval Strategy (eCRS). Treatment-emergent AESIs (based on the latest eCRS at the time of DBL) will be summarized by frequency and percentage of patients by risk name, MedDRA preferred term and by treatment sequence. A listing of the case retrieval strategy will be presented.

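### SAP 8.2 shows adverse event percentages by dose over unequal times (4 against 8 weeks) with no visible exposure adjustment, and shows AESIs by sequence only, so not by dose or period

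*SAP*

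**What the plan says.** SAP 8.2 (Adverse events) gives the number and percentage of patients with an event "with a breakdown by dose for each period separately". An event that runs on into the next period is counted only where it began.

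SAP 1.4 sets the lengths: 4 weeks at the first dose of the sequence (Period 1), 8 weeks at the second (Period 2), then "an approximately 2 year extension Period 3".

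Period 1 can be shorter. Protocol 12.5 foresees this: "In case early escalation gives data only to two weeks for some patients", the modelling is to be adapted. Footnote 2 to Table 8-1 describes the Day 16 visit: "Visit only applicable for Sequence 1 and 2 patients who do not have 40% reduction in LDH level at day 15".

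Protocol 12.5.2 asks for treatment-emergent events "by treatment dose group including split by first and second four weeks in second period". The visible text of SAP 8.2 does not repeat that split. It refers to SAP Section 4, of which one sentence is public and the rest is redacted.

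For AESIs, SAP 8.2 (Clinical Trial Safety Disclosure) says that they "will be summarized by frequency and percentage of patients by risk name, MedDRA preferred term and by treatment sequence". The disclosure tables in the same subsection are by dose and period.

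SAP 8.2 also summarises duration of exposure to each dose and plots days on drug for each patient. No visible text links exposure to event counts.

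**The concern.** Protocol 4.1 gives within-patient comparison as an advantage of the design. For safety, that means reading a patient's first dose against the second, which is Period 1 against Period 2. The second column covers twice the planned time, so a crude percentage can be higher there with no effect of dose.

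Early escalation widens the gap and appears to depend on LDH response. If response differs by dose, the two sequences could also differ in actual Period 1 exposure, although their planned exposure is equal.

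The AESI table has a different fault. It follows the sequence through every dose and the extension, so it cannot place an event at a dose or in a period.

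Safety and tolerability is a secondary objective. The objective does not say by dose, but the safety analyses in both documents do, so those tables should be readable by dose.

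**Working it through.** **Period lengths.** From the visit days in Table 8-1:
- Period 1: (29 − 1)/7 = 4.0 weeks
- Period 2: (85 − 29)/7 = 8.0 weeks
- Period 3: (757 − 85)/7 = 96.0 weeks
- Day 16 visit: (16 − 1)/7 = 2.1 weeks

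These agree with SAP 1.4. The documents give no adverse event rate, so the 4-week risks below are assumptions.

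**Effect of time alone.** Let p4 be the 4-week risk, with constant hazard and no dose effect. Then h = −ln(1 − p4)/4, and the risk over w weeks is 1 − exp(−h·w) = 1 − (1 − p4)^(w/4). For p4 = 20%, the 8-week risk is 1 − 0.8² = 36% and the 2-week risk is 1 − 0.8^0.5 = 10.6%.

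| 4-week risk | 2 weeks | 8 weeks | Ratio 8 to 4 | Ratio 8 to 2 |
|---|---|---|---|---|
| 5% | 2.5% | 9.8% | 1.95 | 3.85 |
| 10% | 5.1% | 19% | 1.90 | 3.70 |
| 20% | 10.6% | 36% | 1.80 | 3.41 |
| 30% | 16.3% | 51% | 1.70 | 3.12 |
| 40% | 22.5% | 64% | 1.60 | 2.84 |
| 50% | 29.3% | 75% | 1.50 | 2.56 |

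If events instead cluster just after each dose starts, the extra weeks add almost nothing and the ratio is close to 1.

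**In patients.** Ten patients at 1:1 give about 5 per sequence. At a 4-week risk of 20%, the expected counts are 5 × 0.20 = 1.0 in Period 1 and 5 × 0.36 = 1.8 in Period 2. Treated as independent binomials (which ignores within-patient correlation), Period 2 shows the higher count with probability 0.59, the lower with 0.17, and a tie with 1 − 0.59 − 0.17 = 0.24.

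**What each remedy does in the 20% case.**
- The protocol's 4-week blocks: among patients still event-free, weeks 1 to 4 of each period have the same 20% risk, a ratio of 1.0. The split does not help when Period 1 stops at about 2 weeks, and it does not remove carry-over or period effects.
- Patients with an event per patient-weeks: Period 1 gives 1.0/(5 × 4) = 5.0 per 100 patient-weeks, and Period 2 gives 1.8/(5 × 8) = 4.5. The ratio falls from 1.8 to 0.9. With a 2-week Period 1 the figure is 5 × 0.106/(5 × 2) = 5.3 per 100.
- The rate can mislead the other way. If events cluster at the start and both periods show 20%, the rates are 1.0/20 = 5.0 and 1.0/40 = 2.5 per 100. It should therefore stand beside the crude percentage and not replace it.

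**AESI table.** A patient who completes Period 3 contributes 4 + 8 + 96 = 108 planned weeks to one sequence column. Of these, 12/108 = 11% fall in Periods 1 and 2, and 96/108 = 89% in the extension. Planned time is the same in both sequences.

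**The case against.** The strongest reply is that the SAP keeps the periods apart. It does not pool 4 and 8 weeks in one cell, and comparing the sequences within a period is matched on planned exposure. That stands. The imbalance appears only when a reader compares across periods, which the SAP does not direct but which the within-patient design invites.

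A reader might infer that the SAP dropped the protocol's 4-week split. The documents do not support this. SAP 8.2 defers to Section 4, which is redacted, and SAP 1.1 says that the SAP implements the protocol's analysis. All that can be said is that the split is not visible in 8.2.

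A reader might also infer that the AESI table makes exposure look like a dose effect. It cannot, because planned time is equal in the two sequences. Its fault is lost attribution. AESI preferred terms should also appear in the general table by dose and period, and Protocol 12.5.2 promises patient-level listings, so the information can be recovered. Recovery is by hand, though: counts of patients cannot be added across preferred terms to give a risk category, because one patient may have several.

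Protocol section 12 says that summaries will respect the distinction between study day and period day where relevant. That helps to assign events to the right period, but it does not equalise exposure.

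Finally, the study is non-confirmatory, open-label and small, and exposure per dose is already summarised. A shift from 1.0 to 1.8 patients out of 5 is modest. This limits the weight of the point but does not remove it.

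**Conclusion.** The point holds as a minor one that is worth acting on. On the visible text, adverse event percentages by dose cover unequal times when first and second doses are compared, with no exposure adjustment. AESIs are shown by sequence with neither dose nor period.

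Under a constant hazard and no dose effect, the 8-week percentage is 1.5 to 1.95 times the 4-week one for assumed 4-week risks of 50% down to 5%. Against a 2-week Period 1 the ratio is 2.56 to 3.85. It is near 1 if events come early after each dose starts. So percentages would be expected to rise under one assumption about timing; it does not follow that they will.

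Two further limits apply. Early escalators might be taken to have 10 weeks at the second dose. That holds only if Period 2 still ends at Day 85, and the visible text describes an 8-week Period 2 without saying what escalation does to its end. The doses and escalation rules are redacted, so treating the second dose as the higher one, or the Day 16 visit as the escalation point, is an inference.

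**What to change.** Make three changes in SAP 8.2:

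1. Tabulate AESIs by risk name and preferred term, by dose at onset and period, as for other adverse events. The sequence table can stay beside it.
2. Beside each crude percentage by dose and period, show patients with an event per patient-weeks at that dose in that period, using actual exposure so that shortened first periods are handled.
3. State that the protocol's split of Period 2 into first and second four weeks applies to the adverse event tables. If Section 4 already says so, a cross-reference is enough.

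No new data are needed, because exposure per dose is already derived. The cost is a few more columns. With about 10 patients the cells will be small and the rates imprecise, so they should be read as description only.
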